The overall study period will be between 2010 and 2020. Different study period starts will be applied depending on which two drugs are being compared. For the comparison between rhFSH-alfa reference product and HP-hMG, the study period will start 1 January 2010 for both countries. This date is selected to ensure the study is sufficiently powered while also reducing heterogeneity in patient management over time. Changes that have occurred over time include moving towards vitrification rather than slow freezing for embryo cryopreservation and hence also moving from cleavage stage to blastocyst embryo transfers, elective single embryo transfers rather than double embryo transfers, and antagonist protocols rather than agonist protocols. For the comparison between rhFSH-alfa reference product and rhFSH-alfa biosimilar products, the study period will start 26 March 2014 for Denmark and 20 June 2014 for Sweden. These are the earliest dates when a rhFSH-alfa biosimilar product (Bemfola) received reimbursement status in each country. For

Sweden, where the IVF register is updated annually and has a lag time of approximately two years (see Section 9.4.2), inclusion of women undergoing IVF/ICSI treatment may end on 31 December 2019, depending on data availability at the time of data extraction. No such general restriction will be applied for Denmark, as the IVF register is updated monthly. In terms of follow-up of IVF/ICSI treatment and pregnancy outcomes, the study will end on 31 December 2020 (or last available date) for each country. Specifically, for the main analyses of the primary objective (LBR, CLBR and MC-CLBR) and secondary objective 4 (TTLB), a minimum follow-up period of 1 year has been chosen to allow sufficient time to achieve (at least) one live birth and a reasonable number of complete cycles for reliable estimates of live birth rates. Hence, the corresponding analyses are restricted to cycles initiated on or before 31 December 2019 (Sets 1 and 5 in Table 5). The minimum follow-up period will be extended to 2 years in a sensitivity analysis to explore the potential effect this has on the estimated MC-CLBR and TTLB (see sensitivity analysis 3 in Table 8).

To reduce possible bias linked to confounding by baseline characteristics, inverse probability of treatment weighting (IPTW), based on propensity scores (PS) (22), will be used to balance the distribution of potential confounders across the study cohorts.

Figure 1. Study design

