9.3.2 Other Variables (Covariates)

In addition to the outcome and exposure variables outlined in Section 9.1.2 and Section 9.3.1, the covariates of interest in this study are listed below and classified according to their intended use in the analysis (Table 1).

The variables are generally described as measured in relation to each IVF/ICSI stimulation cycle; however, variables used to derive the outcome variables may also apply to any linked FET cycles, depending on the outcome under study. Variables indicated as being candidates for regression modeling are determined after the decision on which gonadotropin to use for COS has been made. These variables will therefore not be included in the PS but may instead be added as independent covariates in the IPTW-weighted regression model (see Section 9.7.3.1 for further details).

For variables identified in the registers by ATC, ICD-10 and/or procedure codes, these operational definitions are provided in Appendix 3 (Section 14.3.3).

Table 1. List of covariates and their use in the study

Variable	Measurement scale	Baseline characteristic	Candidate variable for PS	Candidate variable for additional adjustment
Demographic characteristics				
Age at stimulation cycle index date	Continuous	X	X	
IVF/ICSI treatment characteristics				
Treatment type (ICSI, IVF, ICSI + IVF; FET)	Categorical	X	X	
Type of clinic (private, public)	Categorical	X	X	
Calendar year of stimulation cycle	Continuous	X		
GnRH protocol (agonist, antagonist)	Categorical	X	X	
Cycle cancellation (timing within cycle)	Categorical	N/A (used to derive outcome variable)		
Date of cycle cancellation	Continuous	N/A (used to derive outcome variable)		
Type of drug for ovulation triggering	Categorical	X		X

Variable	Measurement scale	Baseline characteristic	Candidate variable for PS	Candidate variable for additional adjustment
Type of drug for luteal phase support	Categorical	X		X
Date of follicular aspiration	Continuous	N/A (used to derive outcome variable)		
Date of embryo transfer	Continuous	N/A (used to derive outcome variable)		
Number of days of embryo cultivation ⁺	Numerical	X		X
Date of embryo cryopreservation	Continuous	N/A (used to derive outcome variable)		
Embryo cryopreservation method (slow freezing, vitrification)	Categorical	X		X
Date of embryo thawing	Continuous	N/A (used to derive outcome variable)		
Number of embryos thawed	Continuous	N/A (used to derive outcome variable)		

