		Per aspirated stimulation cycle	Set 4	Number (see section 9.7.3.3)

Study objective	Outcome	Unit of analysis	Analysis set	Analysis results
				Adjusted OR (see section 9.7.3.4) Stratified analysis (see section 9.7.3.6)
	Number of embryos transferred	Per fresh embryo transfer	Set 6	Number (see section 9.7.3.3) Adjusted OR (see section 9.7.3.4)
		Per frozen embryo transfer	Set 6	Number (see section 9.7.3.3) Adjusted OR (see section 9.7.3.4)
	Number of embryos cryopreserved	Per initiated stimulation cycle	Set 3	Number (see section 9.7.3.3) Adjusted OR (see section 9.7.3.4)
		Per aspirated stimulation cycle	Set 4	Number (see section 9.7.3.3) Adjusted OR (see section 9.7.3.4)
	Number of utilizable embryos	Per initiated stimulation cycle	Set 3	Number (see section 9.7.3.3) Adjusted OR (see section 9.7.3.4)
		Per aspirated stimulation cycle	Set 4	Number (see section 9.7.3.3) Adjusted OR (see section 9.7.3.4)
Secondary objective 3	Implantation rate	Per embryos transferred per stimulation cycle	Set 7	Rate (see section 9.7.3.3) Adjusted OR (see section 9.7.3.4)
Secondary objective 4	Time-to-live birth	Per woman per up to five stimulation cycles with the same drug	Set 8	Kaplan-Meier plots and estimates (see section 9.7.3.5) Adjusted live birth rate ratios (see section 9.7.3.5)
Secondary objective 5	Rate of pregnancy loss	Per clinical pregnancy following embryo transfer	Set 2	Rate (see section 9.7.3.3) Adjusted OR (see section 9.7.3.4)
Secondary objective 6	Multiple pregnancy rate	Per clinical pregnancy following embryo transfer	Set 2	Rate (see section 9.7.3.3) Adjusted OR (see section 9.7.3.4)

Study objective	Outcome	Unit of analysis	Analysis set	Analysis results
Secondary objective 7	Cycle cancellation rate	Per initiated stimulation cycle	Set 3	Rate (see section 9.7.3.3) Adjusted OR (see section 9.7.3.4)
Secondary objective 8	OHSS rate	Per initiated stimulation cycle	Set 5	Rate (see section 9.7.3.3) Adjusted OR (see section 9.7.3.4)
Secondary objective 9	Treatment-associated costs	Per initiated stimulation cycle	Set 2	Descriptive cost analysis (see section 9.7.3.7)

CCPR: cumulative clinical pregnancy rate; CLBR: cumulative live birth rate; CPR: clinical pregnancy rate; COPR: cumulative ongoing pregnancy rate; LBR: live birth rate; MC-CLBR: multiple-cycle cumulative live birth rate; OPR: ongoing pregnancy rate; OHSS: ovarian hyperstimulation syndrome; OR: odds ratio.

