Secondary objective 1	CPR	Number of clinical pregnancies after fresh embryo transfer	Initiated cycles with drug of interest
	CCPR	Number of clinical pregnancies after one initiated stimulation cycle, including all fresh or frozen embryo transfers linked to that cycle	Initiated cycles with drug of interest
	OPR	Number of ongoing pregnancies after fresh embryo transfer	Initiated cycles with drug of interest
	COPR	Number of ongoing pregnancies after one initiated stimulation cycle, including all fresh or frozen embryo transfers linked to that cycle	Initiated cycles with drug of interest
Secondary objective 2	Number of oocytes retrieved	Number of oocytes retrieved	Initiated cycles with drug of interest
		Number of oocytes retrieved	Aspirated cycles with drug of interest

Study objective	Outcome measure	Numerator	Denominator
	Number of embryos transferred	Number of fresh embryos transferred	Fresh embryo transfers linked to cycles with drug of interest
		Number of frozen embryos transferred	Frozen embryo transfers linked to cycles with drug of interest
	Number of embryos cryopreserved	Number of embryos cryopreserved	Initiated cycles with drug of interest
		Number of embryos cryopreserved	Aspirated cycles with drug of interest
	Number of utilizable embryos	Number of utilizable embryos	Initiated cycles with drug of interest
		Number of utilizable embryos	Aspirated cycles with drug of interest
Secondary objective 3	Implantation rate	Number of intrauterine gestational sacs after one fresh or frozen embryo transfer	Number of embryos transferred in one cycle
Secondary objective 4	TTLB	Time to first delivery with at least one live birth in up to five stimulation cycles with the same study drug, including all fresh or frozen embryo transfers linked to each of those stimulation cycles	N/A; conducted as time-to-event analysis; unit of analysis is women who initiated stimulation cycles with drug of interest
Secondary objective 5	Rate of pregnancy loss	Number of induced and spontaneous abortions	Clinical pregnancies with drug of interest following fresh or frozen embryo transfer
Secondary objective 6	Multiple pregnancy rate	Number of multiple pregnancies	Clinical pregnancies with drug of interest following fresh or

Study objective	Outcome measure	Numerator	Denominator
			frozen embryo transfer
Secondary objective 7	Cycle cancellation rate	Number of canceled cycles	Initiated cycles with drug of interest, including any linked initiated FET cycles

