9.7.3.4 Adjusted Odds Ratios

For the comparison of the study cohorts, the ORs (with 95% CI), adjusted for confounding factors, will be estimated by taking into account the IPTWs and using statistical modelling, such as regression analysis or general estimating equations. To estimate the adjusted ORs, the statistical model will be weighted with IPTWs and will include as covariates any variables that were used in the PS but are still unbalanced between the study cohorts after weighting. Statistical models may also be used to additionally adjust the ORs for any other potential covariates that are assessed after the initiation of the IVF/ICSI stimulation cycle and hypothesized to be associated with the given study outcomes (see Table 1 in Section 9.3.2).

For the statistical models, the following study outcomes will be considered as binary outcomes analyzed per fresh embryo transfer: live birth (*i.e.*, a primary objective outcome), clinical pregnancy and ongoing pregnancy (*i.e.*, a subset of secondary objective 1 outcomes). For the statistical models, the following study outcomes will be considered as binary outcomes analyzed per woman: MC-CLBR (*i.e.*, a primary objective outcome) will be analyzed as a binary outcome per woman in statistical models.

For the statistical models, the following study outcomes will be considered as binary outcomes analyzed per clinical pregnancies following fresh or frozen embryo transfer: pregnancy loss (secondary objective 5) and multiple pregnancy (secondary objective 6). Cycle cancellation (secondary objective 7) and OHSS occurrence (secondary objective 8) will be analyzed as binary outcomes per initiated stimulation cycle. Implantation (secondary objective 3) will be analyzed as an ordinal categorical outcome per fresh or frozen embryo transfer.

For the statistical models, the following study outcomes are considered as counts analyzed per initiated stimulation cycle: cumulative live birth (*i.e.*, a primary objective outcome), cumulative clinical pregnancy and cumulative ongoing clinical pregnancy (*i.e.*, a subset of secondary objective 1 outcomes). Also the following study outcomes are considered as counts in statistical models and

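### Implantation rate is defined per embryo transferred, but its adjusted odds ratio comes from an ordinal per-transfer model with no embryo denominator, so the odds ratio does not match the outcome

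*Protocol*

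**What the plan says.** Table 7 (Protocol 9.7.3.3) gives the numerator of the implantation rate as "Number of intrauterine gestational sacs after one fresh or frozen embryo transfer" and the denominator as "Number of embryos transferred in one cycle". Table 6 (9.7.3) gives the unit of analysis as "Per embryos transferred per stimulation cycle" and plans both a rate and an adjusted odds ratio on that unit.

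Section 9.7.3.4 then sets the model behind the odds ratio: "Implantation (secondary objective 3) will be analyzed as an ordinal categorical outcome per fresh or frozen embryo transfer". It does not say what the ordered categories are.

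The same section says the weighted model "will include as covariates any variables that were used in the PS but are still unbalanced between the study cohorts after weighting". It also allows further Table 1 covariates that are measured after the cycle starts. Embryos transferred is not listed in Table 1. The nearest entry, embryos thawed, is there only to derive outcomes and is not a candidate for the propensity score or for adjustment. Calendar year is marked as a baseline characteristic only.

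**The concern.** The rate and the odds ratio for secondary objective 3 answer different questions. The rate asks how likely an embryo is to implant once placed. The ordinal model asks whether a transfer tends to fall in a higher category, and that depends partly on how many embryos were placed. Two embryos have a greater chance of producing at least one sac than one embryo, even when each implants equally well.

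If the share of double transfers differs between the weighted cohorts, the odds ratio moves away from 1 with no difference in implantation per embryo. A real difference could also be masked or reversed, and the reported rates and the odds ratio could then point in different directions.

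Such an imbalance is plausible on the protocol's own account. Section 9.1.1 lists among the changes in practice over time "elective single embryo transfers rather than double embryo transfers". Section 9.9.2 says biosimilar use weighs more heavily in the later years. Calendar year is not a propensity-score candidate, so the weighting does not target a difference tied to time.

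**Working it through.** The protocol states no expected implantation rate, double-transfer share or odds ratio for this outcome, so there is no figure to reproduce. The check below is an illustration, and every numerical input is an assumption.

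**Inputs (assumed).** p is the implantation probability per embryo and d is the share of transfers with two embryos. All other transfers have one embryo, and embryos implant independently.

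**Sacs per transfer.**
- P(0) = (1 − d)(1 − p) + d(1 − p)²
- P(1) = (1 − d)p + 2dp(1 − p)
- P(2) = dp²

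**The defined rate does not depend on d.** Expected sacs per transfer are p(1 + d) and expected embryos per transfer are 1 + d, so the ratio is p. With equal p in the two cohorts, the per-embryo odds ratio is 1.00 whatever the transfer shares.

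**Cell probabilities at p = 0.30.**
- d = 0.30: P(0) = 0.7 × 0.7 + 0.3 × 0.49 = 0.637; P(1) = 0.7 × 0.3 + 0.3 × 0.42 = 0.336; P(2) = 0.3 × 0.09 = 0.027.
- d = 0.20: 0.658, 0.324 and 0.018 by the same formulas.

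**Two possible codings.** Because the categories are undefined, both natural choices were tried: sac count (0, 1, 2) and sacs divided by embryos (0, 0.5, 1). A proportional-odds model with cohort as the only covariate was fitted by maximum likelihood to the expected cell probabilities. The true per-embryo odds ratio is 1.00 in every row.

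| Double-transfer shares (p = 0.30) | Sac-count coding | Ratio coding |
|---|---|---|
| equal | 1.00 | 1.00 |
| 15% vs 10% | 1.06 | 1.02 |
| 30% vs 20% | 1.11 | 1.04 |
| 40% vs 15% | 1.29 | 1.09 |

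**Range over p.** With shares of 10% versus 30% and p from 0.20 to 0.40, the null odds ratio is 0.79 to 0.83 (sac count) or 0.90 to 0.96 (ratio).

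**With a real difference.** Take p = 0.33 versus 0.30. The true odds ratio is (0.33/0.67)/(0.30/0.70) = 1.15. With double-transfer shares of 10% versus 30%, the sac-count model gives 0.93, which reverses the direction, and the ratio model gives 1.08. With equal shares of 10%, both give 1.15.

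**Proportional odds.** For 30% versus 20%, the odds ratio for at least one sac is (0.363/0.637)/(0.342/0.658) = 1.10 under either coding. At the second cut it is (0.027/0.973)/(0.018/0.982) = 1.51 for two sacs. For a ratio of 1 it is 0.89, since P(ratio = 1) = 0.7 × 0.3 + 0.027 = 0.237 versus 0.8 × 0.3 + 0.018 = 0.258. The cut points disagree under both codings, so a single common odds ratio is misspecified when the shares differ.

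**The case against.** Several points on the other side stand.

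- **The coding is open.** Section 9.7.3.4 does not say the categories are sac counts. Ordered values of the Table 7 ratio are also a natural reading, and they carry the denominator. Section 9.1.2.2 ascertains implantation from the number of sacs, which points the other way. A reader might infer that the model ignores the number of embryos altogether, but the text does not establish that. The ratio coding shrinks the distortion without removing it.
- **No imbalance is shown.** A reader might infer that the odds ratio will simply reflect single- versus double-transfer policy. The documents give no transfer shares by product, and with equal shares the null odds ratio is 1.00. Propensity-score candidates such as age, clinic type, parity and earlier failed stimulation may reduce a difference. Section 9.1.1 does not date the move to single transfer within 2010–2020; it cites the move in explaining the 2010 start. A shift in product use is described specifically only for the biosimilars.
- **Cut-point odds ratios are not the result.** Values such as 1.51 (30% versus 20%) or 2.73 (two sacs, 40% versus 15%) belong to the second cut alone. A single ordinal model would not report them, so they overstate the effect.
- **The defined rate is reported too.** Section 9.7.3.3 gives each outcome measure in the original and weighted cohorts, and embryos transferred is compared separately. A difference in transfer number would be visible, but the odds ratio would still not match the rate.
- **Embryos transferred is itself a secondary outcome, measured after treatment.** A difference may be partly an effect of the drug and not only of policy.

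The analysis plan may define the categories. It would still have to depart from the per-transfer ordinal model that the protocol fixes.

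**Conclusion.** The mismatch holds. Tables 6 and 7 define implantation per embryo, while section 9.7.3.4 fixes a per-transfer ordinal model with undefined categories and no specified denominator. This is a stated choice of model, and neither natural coding makes its odds ratio estimate the defined outcome.

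Any bias is conditional on the weighted cohorts differing in their double-transfer shares, which the documents make plausible but do not show. For the assumed share differences of 5 to 25 percentage points in the table, the null odds ratio is off by about 2% to 29%, depending on the coding and the gap. These figures rest on 30% implantation per embryo, at most two embryos per transfer and independent implantation. One secondary outcome is affected, and the primary live birth results are not touched. The change should be made.

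**What to change.** Replace the implantation sentence in section 9.7.3.4 with an IPTW-weighted grouped-binomial (logit) model of gestational sacs out of embryos transferred, fitted by GEE clustered on the woman and allowing overdispersion. Add a rule, such as capping or flagging, for the rare transfers with more sacs recorded than embryos. In the null scenarios above, the odds ratio is then 1.00 whatever the double-transfer shares; for 33% versus 30% it is 1.15.

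The cost is one sentence. Sacs and embryos transferred are already collected, and the section already allows estimating equations. The downside is that the per-embryo odds ratio conditions on a post-treatment outcome. The Table 7 definition already does this, so the result should be read beside the separate analysis of embryos transferred.

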8.1 Primary Objective

The primary objective of this study is to compare rhFSH-alfa reference product with HP-hMG or rhFSH-alfa biosimilar products regarding the following live birth outcome measures:

- a) LBR per initiated IVF/ICSI stimulation cycle
- b) CLBR per initiated IVF/ICSI stimulation cycle
- c) CLBR in up to five initiated IVF/ICSI stimulation cycles [termed multiple-cycle (MC-)CLBR]

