9.1.2.1 Primary

The primary outcome of this study is live birth. It is defined generally as the complete expulsion or extraction from a woman of a product of fertilization, after 22 completed weeks of gestational age; which, after such separation, breathes or shows any other evidence of life, such as heartbeat, umbilical cord pulsation or definite movement of voluntary muscles, irrespective of whether the umbilical cord has been cut or the placenta still attached or not (16).

Information on live birth will be obtained from the medical birth register in each country and the IVF register in Sweden. Only live births that can be linked to a given IVF/ICSI stimulation cycle included in the study will be considered. The live birth of multiples will be counted as one live birth in this study.

For the assessment of the primary objective and secondary objective 4, the different measures of live birth are defined as follows:

- LBR is the probability of a live birth after one initiated stimulation cycle, considering fresh embryo transfer.
- CLBR is the number of live births per initiated stimulation cycle, considering all fresh and subsequent frozen embryo transfers linked to that stimulation cycle and counting all live births from the same transfers.
- MC-CLBR is the probability of a live birth in up to five stimulation cycles, considering all fresh and subsequent frozen embryo transfers linked to each of those stimulation cycles, until the first live birth occurs.
- TTLB is the time (in number of cycles) until live birth in up to five stimulation cycles, considering all fresh and subsequent frozen embryo transfers linked to each of those stimulation cycles, until the first live birth occurs.

For the calculation of the above measures, refer to Section 9.7.3.3 (Table 7).

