9.7.3 Statistical Methods

For the primary objective, the main data analysis will be conducted in two stages: (i) construction of the IPTW-weighted study cohorts by modelling the rhFSH-alfa reference product vs. HP-hMG stimulation cycle initiation and rhFSH-alfa reference product vs. rhFSH-alfa biosimilar product stimulation cycle initiation, (ii) estimating the effect of rhFSH-alfa reference product on the (cumulative) live birth rates using adjusted (IPTW-weighted) odds ratios (ORs), comparing rhFSH-alfa reference product study cohort to the comparators (HP-hMG study cohort or rhFSH-alfa biosimilars study cohort). The IPTW-weighted study cohorts will also be used for the secondary objectives to estimate the effect of rhFSH-alfa reference product on the secondary outcomes, comparing rhFSH-alfa reference product study cohort with the comparators (HP-hMG study cohort or rhFSH-alfa biosimilars study cohort).

Table 6 below summarizes the data analysis planned for the study and an overview of the planned analysis is given in the subsections below. Further details of the statistical analysis will be provided in the SAP.

Table 6. Overview of planned statistical analysis per outcome measure

Study objective	Outcome	Unit of analysis	Analysis set	Analysis results
Primary objective	LBR	Per initiated stimulation cycle	Set 1	Rate (see section 9.7.3.3) Adjusted OR (see section 9.7.3.4) Stratified analysis (see section 9.7.3.6)
	CLBR	Per initiated stimulation cycle	Set 2	Rate (see section 9.7.3.3) Adjusted OR (see section 9.7.3.4) Stratified analysis (see section 9.7.3.6)
	MC-CLBR	Per woman	Set 8	Rate (see section 9.7.3.3) Adjusted OR (see section 9.7.3.4)
Secondary objective 1	CPR	Per initiated stimulation cycle	Set 1	Rate (see section 9.7.3.3) Adjusted OR (see section 9.7.3.4) Stratified analysis (see section 9.7.3.6)
	OPR	Per initiated stimulation cycle	Set 1	Rate (see section 9.7.3.3) Adjusted OR (see section 9.7.3.4) Stratified analysis (see section 9.7.3.6)
	CCPR	Per initiated stimulation cycle	Set 2	Rate (see section 9.7.3.3) Adjusted OR (see section 9.7.3.4) Stratified analysis (see section 9.7.3.6)
	COPR	Per initiated stimulation cycle	Set 2	Rate (see section 9.7.3.3) Adjusted OR (see section 9.7.3.4) Stratified analysis (see section 9.7.3.6)
Secondary objective 2	Number of oocytes retrieved	Per initiated stimulation cycle	Set 3	Number (see section 9.7.3.3) Adjusted OR (see section 9.7.3.4) Stratified analysis (see section 9.7.3.6)

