9.7.3.3 Rates and Numbers

The results of the study outcomes in the study cohorts will be estimated by calculating the outcome measures according to their definitions (see Table 7) in both original and IPTW-weighted study cohorts.

For the analyses of LBR, a woman may contribute up to one delivery resulting in live birth. For the analyses of CLBR, a woman may contribute several deliveries resulting in live birth per each stimulation cycle. The same principle applies to the analyses of clinical and ongoing pregnancies, *i.e.*, a woman may contribute several clinical and ongoing pregnancies for the analyses of CCPR and COPR, respectively.

For the analysis of MC-CLBR, where the woman is the unit of analysis, only the first occurrence of a live birth per woman within the first five stimulation cycles using the same study drug will be considered. The MC-CLBR analysis will be performed by cycle rank, *i.e.*, analyzed as the cumulative probability of a live birth up to and including the first, second, third, fourth and fifth stimulation cycle, respectively. The MC-CLBR analysis will be restricted to women who initiated their first-ever stimulation cycle during the study period.

In the assessment of MC-CLBR, it is assumed that women who did not return during the study period for another stimulation cycle after a failed attempt (*i.e.*, who did not have a live birth), did not have any live birth. Thus, for the main analysis, the MC-CLBRs will be calculated as conservative estimates (20). Optimal estimates will be provided in a sensitivity analysis restricted to the primary objective (see Analysis 2 Section 9.7.3.9).

Rates and numbers will be expressed as the rate or number per 100 units of observations with 95% CI.

Table 7. Definitions of outcome measures

Study objective	Outcome measure	Numerator	Denominator
Primary objective	LBR	Number of deliveries with at least one live birth after fresh embryo transfer	Initiated cycles with drug of interest
	CLBR	Number of deliveries with at least one live birth after one initiated stimulation cycle, including all fresh or frozen embryo transfers linked to that cycle	Initiated cycles with drug of interest
	MC-CLBR	Number of deliveries with at least one live birth after each initiated stimulation cycle in up to five cycles, including all fresh or frozen embryo transfers linked to each of those stimulation cycles	Women who initiated 1, 2, 3, 4 or 5 cycles with drug of interest

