will be analyzed both per initiated stimulation cycle and per aspirated stimulation cycle: number of oocytes retrieved and number of utilizable embryos (*i.e.*, a subset of secondary objective 2 outcomes). Number of embryos transferred (*i.e.*, a secondary objective 2 outcome) will also be considered as a count outcome in statistical models and will be analyzed per fresh and frozen embryo transfers. For modelling the count data appropriately, the distribution of count data will be checked by counting the mean and the variance of the data and the possibility of excess zeros in the count data will be evaluated visually by plotting the distribution of the data.

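### CLBR, a primary outcome, is modelled as a count but its effect is reported as an adjusted odds ratio, and the protocol does not say how one gives the other; several secondary counts share the mismatch.

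*Protocol*

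**What the plan says.** CLBR is item (b) of the primary objective (section 8.1): "CLBR per initiated IVF/ICSI stimulation cycle". Section 9.1.2.1 defines LBR and MC-CLBR as probabilities of a live birth, but CLBR differently: "CLBR is the number of live births per initiated stimulation cycle". Section 9.7.3.3 confirms that more than one event per cycle can count: "a woman may contribute several deliveries resulting in live birth per each stimulation cycle".

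Section 9.7.3.4 carries this into the model: "the following study outcomes are considered as counts analyzed per initiated stimulation cycle: cumulative live birth", with cumulative clinical and cumulative ongoing pregnancy in the same list. Oocytes retrieved, utilizable embryos and embryos transferred follow as counts. The planned checks are those of a count model: mean against variance, and "the possibility of excess zeros in the count data will be evaluated visually by plotting the distribution of the data".

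The effect measure is an OR throughout. Section 9.7.3 describes the second stage of the primary analysis as "estimating the effect of rhFSH-alfa reference product on the (cumulative) live birth rates using adjusted (IPTW-weighted) odds ratios (ORs"), and the abstract says the same. Table 6 enters an adjusted OR for CLBR, CCPR, COPR and every oocyte and embryo outcome. Section 9.7.3.4 is itself titled for odds ratios, and section 9.7.3.6 promises adjusted odds ratios for the stratified analyses of CLBR, CCPR, COPR, oocytes and utilizable embryos.

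For implantation, Table 7 gives gestational sacs over embryos transferred, while section 9.7.3.4 says it "will be analyzed as an ordinal categorical outcome per fresh or frozen embryo transfer".

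**The concern.** The protocol fixes both the type of outcome (count) and the effect measure (OR), and the two do not fit. A Poisson or negative binomial model with log link estimates a ratio of mean counts. An OR compares the odds of a yes/no event, and for CLBR no such event is defined.

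Three things are at stake. A mean ratio printed under an OR label would be read beside the LBR and MC-CLBR results, which are genuine ORs. If the mismatch is settled only after data access, by splitting the count into yes/no or by choosing a model that happens to yield an OR, a primary estimand is chosen late. And the meta-analysis of the primary objective (section 9.7.3.8) needs one named measure for CLBR in both countries.

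**Working it through.** **Is there a bridge from count to OR?** Reading sections 9.1.2.1, 9.7.3, 9.7.3.3, 9.7.3.4, 9.7.3.6, Tables 6 and 7 and the abstract side by side:

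| Outcome | Model type in 9.7.3.4 | Effect in Table 6 |
|---|---|---|
| LBR, MC-CLBR | binary | adjusted OR (fits) |
| CLBR, CCPR, COPR | count per initiated cycle | adjusted OR (no fit) |
| Oocytes retrieved, utilizable embryos, embryos transferred | count | adjusted OR (no fit) |
| Embryos cryopreserved | none named | adjusted OR |
| Implantation | ordinal per transfer | adjusted OR (an ordinal model can give one) |

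No section turns CLBR into a yes/no outcome, names a mean or rate ratio for it, or names a count model that returns an OR. The only ratio other than an OR is the Cox rate ratio for time-to-live birth (section 9.7.3.5).

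**How far apart are the two measures?** The protocol gives no CLBR figure to reproduce; the 50% in section 9.5 is for MC-CLBR. The CLBR levels below are therefore assumptions. Let p0 and p1 be the shares of cycles with at least one live-birth delivery (comparator, reference), and q0 and q1 the shares of those with a second delivery.

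- Mean count: m = p(1 + q). Mean ratio: MR = m1/m0.
- OR for at least one delivery: p1(1 − p0) / [p0(1 − p1)].

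With q0 = q1, MR = p1/p0:

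| p0 | p1 | MR | OR |
|---|---|---|---|
| 25% | 26.5% | 1.060 | 1.082 |
| 30% | 31.5% | 1.050 | 1.073 |
| 35% | 36.75% | 1.050 | 1.079 |
| 35% | 38.5% | 1.100 | 1.163 |
| 45% | 49.5% | 1.100 | 1.198 |
| 50% | 51.5% | 1.030 | 1.062 |

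For the fourth row: 0.385 × 0.65 / (0.35 × 0.615) = 0.25025 / 0.21525 = 1.163.

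**Size of a mislabel.** MR − 1 = (p1 − p0)/p0 and OR − 1 = (p1 − p0)/[p0(1 − p1)], so (MR − 1)/(OR − 1) = 1 − p1. A mean ratio printed as an OR thus understates the excess over 1 by the fraction p1: 36.75% and 38.5% in the two 35% rows, and 49.5% in the 45% row. A reader who took 1.10 as an OR at 35% would compute odds of 0.5385 × 1.10 = 0.5923, hence p1 = 0.5923/1.5923 = 37.2%. That is a difference of 2.2 points where the true one is 3.5.

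**Second deliveries.** If the shares differ, the order can reverse. With p0 = 30%, q0 = 5%, p1 = 31.5%, q1 = 10%: m0 = 0.315, m1 = 0.3465, MR = 1.100, while the OR for at least one delivery is 1.073. No fixed conversion links the two measures.

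**The case against.** The strongest reply is that section 9.7.3.4 leaves the model open and plans to look for excess zeros before choosing it. The zero part of a hurdle model, or a proportional-odds model, would give an OR, and the protocol refers further detail to the SAP. This stands to a degree: a reader might infer that the CLBR estimate cannot be produced at all, and the document does not support that. But neither model is named for CLBR, and the ordinal approach is named only for implantation. The two also target different quantities, so choosing between them is more than a detail. With a standard count model, the SAP cannot honour both statements.

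It is also fair that counting every delivery is deliberate, being stated in both 9.1.2.1 and 9.7.3.3. The count definition is therefore not an error, and a binary CLBR is one acceptable repair rather than the required one.

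Other stronger readings go too far:

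- That implantation would reward double embryo transfer. Section 9.7.3.4 does not define the ordinal categories; they could be sacs per embryo.
- That the count rewards cycles with longer time to use frozen embryos. Unequal follow-up is a separate matter, acknowledged in section 9.9.2, and would also touch a binary CLBR without a fixed window.
- That pooling would be invalid. Nothing suggests that CLBR is pooled with LBR or MC-CLBR; if both countries use the same measure, only the label is wrong.

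**Conclusion.** The contradiction is real and lies within the protocol. For one of the three primary measures, and for CCPR, COPR, oocytes retrieved, utilizable embryos and embryos transferred, the stated effect measure does not follow from the stated outcome type. Embryos cryopreserved has an OR in Table 6 and no model type, which is a gap in the same section rather than the same conflict.

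The size depends on assumptions. At an assumed comparator CLBR of 35% with no second deliveries, 1.10 as a mean ratio is 1.16 as an OR. Over the levels tried (25% to 50%), the two differ for every effect shown. A reader might infer that a mislabel always distorts the effect by more than half. In the direction at issue, a mean ratio called an OR, that holds only if the CLBR in the reference cohort exceeds 50%, and only when second-delivery shares are equal. When they differ, even the direction can change. Study size is unaffected, because section 9.5 uses MC-CLBR, which is binary per woman.

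**What to change.** Before data access, choose one of two repairs for CLBR, CCPR and COPR:

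- **(a) Keep the count.** State an IPTW-weighted adjusted mean (rate) ratio in the abstract, 9.7.3, 9.7.3.4, 9.7.3.6, Table 6 and the meta-analysis section (9.7.3.8).
- **(b) Make the comparison binary.** Compare at least one live-birth delivery (or pregnancy) per initiated stimulation cycle by IPTW-weighted logistic regression or GEE with an OR. Keep the number of deliveries as a supplementary analysis with a mean ratio. This touches 9.1.2.1, 9.1.2.2, 9.7.3.3, 9.7.3.4 and Table 7.

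In either case, change Table 6 (and 9.7.3.6 where it applies) from OR to mean ratio for oocytes retrieved, utilizable embryos and embryos transferred. List embryos cryopreserved among the counts in 9.7.3.4 with the same measure.

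As a secondary point, align the implantation model with Table 7, for example as a grouped binomial of sacs out of embryos transferred.

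The cost is wording only, with no new data. Under (a), CLBR is no longer on the same scale as LBR and MC-CLBR. Under (b), second births from one stimulation leave the primary comparison.
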